Following research ethics board approval, data will be extracted from Cerner Surginet Anesthesia (intraoperative electronic records) and Cerner PowerChart (preoperative and postoperative electronic records). The extracted data will consist of cohort characteristics (patient, anesthetic, surgical variables relevant to MINS (see Data Dictionary below), and patient vital signs with time stamps up to postoperative day 3. The time series time stamps will be transposed to have the start of surgery as 00:00, Jan 1, 2020. A manual chart review will also be performed to extract data not automatically retrieved from Cerner and Surginet (e.g. diagnoses of morbidities). We will extract relevant preoperative comorbidities, including RCRI and Charlson Comorbidity Index categories that are available to the Cerner team via CIHI with no date limit to obtain all preoperative comorbidities (please see Appendix). The Cerner, Surginet, and chart review data will then be linked by de-identified study ID and full surgery date.

Duration of data collection

Preoperative laboratory values are collected within 30 days before surgery. Preoperative vitals are collected within 24 hours before surgery. The total duration of subsequent data collection will be from the time of surgery up to postoperative day 3 (since the MINS protocol monitors for 3 days) or hospital discharge or death, whichever occurs first. Since 90% of MINS happen between postoperative days zero and two (4) and the frequency of monitoring would likely decrease by postoperative day 3, we will model troponin from postoperative day 0 to postoperative day 2 for the primary analysis to balance utility of the temporal model and prediction data quality.

Outcome

In the primary model, we will model high-sensitivity troponin (hsTnT) level as a continuous outcome, such that the model will remain useful if the troponin threshold definitions for MINS evolve.

In the secondary model, we will use the American Heart Association (AHA) definitions (6) for MINS, briefly:

1. Postoperative hsTnT 20 to <65 ng/L with an absolute increase of ≥ 5 ng/L amongst any postoperative troponins, or ≥ 65 ng/L, “attributable to a presumed ischemic mechanism (ie, supply-demand mismatch or atherothrombosis) in the absence of an overt precipitating nonischemic cause (eg, pulmonary embolism)”. The timestamp for laboratory diagnosis will be set at the time that the sample of elevated troponin was drawn.

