- Summary predictor variables as defined by clinicians based on literature (e.g. duration MAP<75, duration HR >100) - different thresholds will be explored
 - **For the primary model, duration MAP<75 will be used (Liem et al.)**
 - Since vitals on the surgical ward may not be measured as frequently, episodes will be defined with the first low value as the start of the event and the first next measurement that is normal as the end of the event.
- Univariate time series (machine learning)
- Multivariate time series (machine learning)

Table 4. Examples of summary variables for vital signs.

These will be modeled based on time stamps as: 1) intraoperative only, 2) postoperative only, and 3) both intraoperative and postoperative periods

Blood pressure	
SBP
 
 1. Maximum decrease from preoperative (defined as median past 24h throughout this table) SBP, as a) absolute change (mmHg), and b) relative change (%) 2. Cumulative duration (minutes) 20% below preoperative preoperative SBP 3. Longest single episode (minutes) below a) 80, b) 90, and c)100 mmHg 4. Cumulative duration (minutes) below a) 80, b) 90, and c)100 mmHg 
MAP
 
 1. Maximum decrease from preoperative MAP, as a) absolute change (mmHg), and b) relative change (%) 2. Cumulative duration (minutes) 20% below preoperative MAP 3. Longest single episode (minutes) below a) 60, b) 65, c) 70, d) 75, e) 80, and f) 85mmHg 4. Cumulative duration (minutes) below a) 50, b) 60, c) 65, d) 70, e) 75, f) 80, and g) 85mmHg
-----------------------	--

Heart rate	
 1. Maximum decrease from preoperative heart rate, as a) absolute change (beats per minute, BPM), and b) relative change (%) 2. Maximum increase from preoperative heart rate, as a) absolute change (BPM), and b) relative change (%) 3. Maximum pulse variation (maximum heart rate minus minimum heart rate) 4. Longest single episode (minutes) below 40, 50, or 60, and above 100, 110, or 120 BPM 5. Cumulative duration (minutes) a) below 60, and b) above 100BPM
Oxygen saturation by pulse oximetry: SpO₂	
 1. Longest single episode (minutes) below a) 88, and b) 90% 2. Cumulative duration (minutes) below a) 88, and b) 90% 3. New postoperative requirement for supplementary oxygen

Other candidate features

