***A priori* features in the primary model**

This *a priori* list of predictors will be used for the primary modeling in Objective 1: duration hypotension (summarized as a percentage of duration of MAP<75 mmHg in the duration of time modeled, e.g. postoperative day 0, 1, and 2), age, sex, emergency surgery, RCRI, and postoperative GFR, as well as the postoperative day and the interaction between postoperative day and % duration MAP<75mmHg as detailed below.

Statistical analysis

Missing data

We will exclude patients with no intraoperative or postoperative vital signs and no troponin measurements from the cohort. Complete case analysis will be performed for vital sign features, with each complete case defined as a patient with ≥ 1 vital sign measurement(s) and ≥ 1 troponin measurement(s). Since the frequencies of measurements are different, missing vital signs are not considered missing values for inclusion/exclusion purposes as long as patients meet the complete case criteria. No imputation will be performed for vital sign data.

For features that are not vital signs (e.g. age, sex), we anticipate minimal missing data (as these variables are routinely collected), and assume missing at random. Due to the longitudinal data structure with correlated observations, we opted for a simpler method of imputation for the primary analysis. For features missing $< 1\%$, complete case analysis will be

performed; between 1-<10%, multiple imputation; above 10%, the feature would be excluded from the model and the reason for missing data will be investigated.

Data quality

The data quality of the CIHI vs. chart review results of the comorbidity information will be assessed by Pearson correlation, with chart review as the gold standard.

Cohort characteristics

Continuous data will be presented in mean (SD) if normal, and median (IQR) if non-normally distributed. Categorical data will be presented as frequency (%). The following characteristics will be presented as overall group, and stratified by MINS vs. no MINS:

- Age
- Gender
- American Society of Anesthesiologists' physical status classification (ASA)
- Type of anesthesia (general, neuraxial, peripheral, and/or sedation)
- RCRI score and categories: pre-existing TIA/CVA, insulin dependent diabetes, serum creatinine >177 mmol/L, coronary artery disease, congestive heart failure, and high risk surgery including intrathoracic, intraabdominal or suprainguinal vascular surgery

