The Cerner, Surginet, and chart review data will then be linked by de-identified Cerner study ID. The time series time stamps will be shifted to have the start of surgery as 00:00, Jan 1, 2020, in order to standardize the times for longitudinal modeling. Data will then be processed for removal of vital sign artefacts per the Multicentre Perioperative Outcomes Group protocol (35). To generate a final blood pressure dataset, if noninvasive blood pressure and invasive blood pressure are available during the same minute, then the measurement that is 1) not marked as artefact and 2) has a higher systolic blood pressure will be taken. Data will also be processed for calculation of RCRI, determination of the timing of MINS diagnosis, truncation of vital sign time series to the appropriate time stamp (see below), and calculation of duration under threshold of the time series to create vital sign summary variables as described in Table 4 for each postoperative day (0-<24h, 24-<48, 48-<72, and <72-96h after surgery end time). A formal chart review will also be performed to extract data not automatically retrieved from Cerner and Surginet, and verify data quality of automatically extracted comorbidities.

For modeling troponin as a continuous outcome, the vital sign time series will be truncated at the last troponin measurement within 3 days of surgery. For modeling the binary MINS outcome definitions the data will be truncated at the time of troponin laboratory diagnosis of the outcome event, postoperative day 3 (since the MINS protocol monitors for 3 days) or hospital discharge or death, whichever occurs first. All time measurements will be standardized as above in relation to the surgery start time.

Predictive Modeling Approaches

Approach I. Analysis using conventional longitudinal modeling (primary objective)

Data visualization

The initial exploratory analysis of the vital signs and troponin data involves time series visualizations and summaries to explore any potential patterns present in the data that may be associated with troponin quantiles or MINS or myocardial injury diagnosis. Spaghetti plots of the longitudinal data will be created for the outcome and vital signs variables, with lines colour-coded by troponin quantiles or MINS or myocardial injury diagnosis. Other relevant visualizations (scatterplots, boxplots, etc.) examining the associations between the troponin outcome and the vital signs variables will also be created.

Primary Modeling

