The primary analysis will involve building a linear mixed effects model (with random intercepts) to predict the maximum daily troponin level between postoperative days 0 to 2 as the continuous outcome. The postoperative days 0, 1, and 2 accounts for approximately 40%, 40%, and 10% of MINS, respectively (4). Due to the limitations in retrospective data and the daily troponin monitoring, we will use day as a unit for time rather than hour to avoid overestimation of precision by readers.

For the primary and secondary models described in Objectives 1 and 2, an *a priori* list of predictors will be used: duration hypotension (summarized as a percentage of duration of MAP<75 mmHg in the duration of time modeled, e.g. postoperative day 1) age, sex, emergency surgery, RCRI, and postoperative GFR, as well as the postoperative day and the interaction between postoperative day and % duration MAP<75 mmHg as detailed below.

For longitudinal modeling, the vital signs data and troponin data will be aggregated to the day level, so that the model can predict at the daily temporal level. If there are multiple troponin measurements on the same day, the maximum will be taken. This aggregation of the data is necessary to account for the fact that the vital signs and troponin measurements are measured at irregular intervals (both across patients and data types), often due to the acting physician's response to the patient's condition. Additionally, due to this characteristic of the raw data, the vital signs predictors will be created such that they are standardized to be robust to the number of daily measurements performed (for example, by taking the percentage of day duration, NOT the total duration, of blood pressure below a specific threshold across all measurements during that day). A categorical time variable (representing the day of the measurement) will be included as a predictor within the model.

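### Percentage of day with MAP below 75 mmHg is not robust to how often BP is read, because each low reading counts until the next normal one with no maximum gap

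*Combined protocol and SAP*

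**What the plan says.** The section on vital sign candidate features sets the episode rule: "episodes will be defined with the first low value as the start of the event and the first next measurement that is normal" as its end. The reason given is "Since vitals on the surgical ward may not be measured as frequently". No maximum gap is stated. Nor does the plan say how to close a low episode that has no later normal reading before the day ends or the series is truncated.

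The a priori feature list uses this as the hypotension predictor, "summarized as a percentage of duration of MAP<75 mmHg in the duration of time modeled". Primary Modeling applies the same list to Objectives 1 and 2. It states that "the vital signs predictors will be created such that they are standardized to be robust to the number of daily measurements performed", and gives the means: "by taking the percentage of day duration, NOT the total duration, of blood pressure below a specific threshold". The same paragraph says that vital signs and troponin are measured at irregular intervals, "often due to the acting physician's response to the patient's condition". Data processing sets the day windows at "0-<24h, 24-<48, 48-<72, and <72-96h after surgery end time".

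The planned look at vital sign frequency is a plot by postoperative day under Cohort characteristics. Missing data says that vital signs will not be imputed.

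**The concern.** The episode rule is in effect last value carried forward for low readings. The measured duration therefore depends on the gap to the next reading as well as on the patient's pressure. A percentage of a full day divides every patient's duration by the same number, so it cannot remove that dependence.

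The measurement error then differs between densely monitored patients (theatre, HAU, ICU) and ward patients, who share one coefficient. A day term can absorb average differences between days, but not differences between settings on the same day. Primary Modeling also interprets the BP and BP-by-day coefficients as effects of BP on each day. Objective 3 asks whether intraoperative or postoperative hypotension alone suffices. If theatre readings are denser than ward readings, as the plan implies, the postoperative predictor is measured with more error, and the comparison is partly one of sampling density.

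**Working it through.** The plan gives no figure to reproduce.

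**Inputs.** From the documents: the episode rule; a 24-hour window of 1440 min; BP resolved to the minute where dense (Data processing). Not in the documents, so assumed: reading intervals from 5 min to 8 h; and two forms of MAP process.
- Continuous: patient means 88 (SD 7), within-day SD 9, autocorrelation time 120 or 30 min, about 13% of time below 75.
- Two-state: 5% or 10% of time low, mean low spell 20 to 180 min.

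**1. One isolated low reading.** With readings every g minutes the score is 100 × g/1440.
- g = 5: 0.35%
- g = 60: 4.2%
- g = 240: 16.7%
- g = 480: 33.3%

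From 5 min to 4 h the ratio is 240/5 = 48.

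**2. Why the average need not be inflated.** A true 30-min dip is 30/1440 = 2.1% of the day. At 4-hourly readings with random phase it is caught with probability 30/240 = 0.125 and then scores 16.7%. The expected score is 0.125 × 16.7% = 2.1%, which is correct on average. But the single patient-day scores either zero (88% of the time) or about eight times the truth. At 8-hourly it is missed with probability 1 − 30/480 = 0.94. In the two-state simulation with fixed schedules, measured mean over true mean was 0.95-1.00.

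**3. Effect on the coefficient.** The slope of true on measured percentage is the factor by which a linear coefficient is multiplied (1 = undistorted). Ranges span repeated runs or the assumed spell lengths.

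| Reading pattern | Continuous, 120 min | Continuous, 30 min | Two-state |
|---|---|---|---|
| 4-hourly, no rechecks | 0.75-0.77 | 0.58-0.62 | 0.67-0.91 |
| 8-hourly, no rechecks | not tabulated | not tabulated | 0.47-0.72 |
| 4-hourly, half of lows rechecked | 0.89 | 0.82 | not run |
| 4-hourly, every low rechecked at 60 min | 1.25 | 1.45 | 1.24-1.65 |
| 4-hourly, every low rechecked at 30 min | 1.44-1.57 | 1.91-2.12 | 1.32-2.53 |

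The two-state values above 2.1 come from low spells averaging 20 or 30 min. Rechecks at 15 min push that process further, to 3.67 at most.

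**4. Effect on the mean when lows are rechecked.** With a 4-hourly schedule and every low rechecked at 15-60 min, the two-state measured mean is 0.14-0.65 of the truth. In the continuous process with 30-min rechecks, a true mean of about 13% is measured as 4.8-5.1% (120 min) or 3.0% (30 min).

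**5. Linear interpolation instead.** With every low rechecked at 30 min on a 4-hourly schedule, the slope becomes 0.91-0.99 (120 min) and 0.94-1.04 (30 min). In a cohort mixing dense and ward sampling (30 min autocorrelation), correlation with the true percentage rises from 0.82 to 0.84 without rechecks, and from 0.72 to 0.85 with full rechecks.

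**The case against.** The strongest reply is that this is a prediction study, judged by RMSE, R-squared, AUC and calibration. A coefficient for the charted predictor is not wrong, under the same charting, merely because it differs from the coefficient for unobserved true hypotension. Under one uniform pattern with full rechecks, correlation with the truth barely differs between the plan's rule and interpolation: 0.87 against 0.90 (120 min), and 0.80 against 0.81 (30 min). This stands in part: no loss of predictive performance has been demonstrated. It does not cover a cohort that mixes settings, where the correlations separate, or the plan's own reading of the coefficients as BP effects.

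The plan also offers partial cover: an ICU subgroup if sample size allows, separate intraoperative and postoperative models, summaries such as maximum fall from preoperative MAP that do not use the episode rule, and raw time-series models. The percentage form does help when a window is cut short. None of these repairs the primary predictor or makes the robustness statement true.

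The size is easily overstated. With half of low readings rechecked, the plan's rule gives slopes of 0.89, 0.82 and 1.00 (autocorrelation 120, 30 and 360 min). Interpolation gives 0.81, 0.73 and 0.89, so the plan's rule is closer to 1 there.

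A reader might also infer that the day-by-BP interaction is an artefact of BP charting that thins out over days, citing "the frequency of monitoring would likely decrease by postoperative day 3". That sentence justifies modelling troponin on days 0 to 2 and concerns day 3, which the primary model omits. It does not show BP frequency falling across days 0 to 2.

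**Conclusion.** The contradiction is certain from the text: the episode rule makes the predictor depend on reading frequency, and a percentage of the day does not undo that. The 0.35%, 16.7% and 33.3% scores are arithmetic, given the intervals.

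The effect on the models is conditional. With timing unrelated to BP, expect noise and a coefficient about 0.6-0.9 of its true size at 4-hourly readings. With early rechecks, which the plan's remark on condition-driven timing makes plausible, expect undercounting. Inflation of about 1.2-2.1 times (more with very short low spells) needs the extreme case in which every low reading is rechecked. All these sizes rest on assumed intervals and MAP processes.

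Two stronger readings are not supported. Sparse readings do not always overstate hypotension, because missed dips offset overcounted ones and rechecks push the measure down. Nor can one say that the true effect is off by −40% to +100% from charting alone: that span joins the no-recheck and all-recheck extremes at the shorter autocorrelation time. The point merits a change to the SAP. It does not invalidate the study.

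**What to change.** 1. Delete or correct the robustness statement in Primary Modeling. A percentage adjusts for window length, not for number of readings.
2. Compute percentage of time with MAP below 75 by linear interpolation between successive valid readings, over observed time. State how intervals at day boundaries and truncation are handled. Reconcile this with the no-imputation statement under Missing data, noting that the present rule also fills the gaps between readings.
3. Report the models under both the interpolated and the carry-forward definitions. Compare RMSE or AUC, calibration, and the BP and BP-by-day terms.
4. Add an exploratory model with care setting or number of BP readings that day. HAU and ICU times are already in the data dictionary. Read it with caution: reading count is partly caused by hypotension, so whether the BP terms survive is not a clean test.

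**Cost.** Some code, SAP wording and extra output; no new data. The linear model has 10 coefficients if RCRI is one term (BP, two day terms, two interactions, age, sex, emergency surgery, RCRI, GFR), so reading count makes 11 against the cap of 15. The binary model already lists 8 variables against its cap of 8, so the added term there should be labelled as exceeding it.

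**Limits of interpolation.** It understates short dips and lowers the mean: 10.2% against a true 12.5% with hourly readings at 30 min autocorrelation, and 10.1% against 12.7% at regular 4-hourly. It does not cure attenuation under regular sparse sampling (0.79 against 0.77 at 4-hourly, 120 min). With 8-hourly readings and full 30-min rechecks its slope is only about 0.66-0.74. Hence both definitions should be reported.

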***A priori* features in the primary model**

This *a priori* list of predictors will be used for the primary modeling in Objective 1: duration hypotension (summarized as a percentage of duration of MAP<75 mmHg in the duration of time modeled, e.g. postoperative day 0, 1, and 2), age, sex, emergency surgery, RCRI, and postoperative GFR, as well as the postoperative day and the interaction between postoperative day and % duration MAP<75mmHg as detailed below.

Statistical analysis

Missing data

We will exclude patients with no intraoperative or postoperative vital signs and no troponin measurements from the cohort. Complete case analysis will be performed for vital sign features, with each complete case defined as a patient with ≥ 1 vital sign measurement(s) and ≥ 1 troponin measurement(s). Since the frequencies of measurements are different, missing vital signs are not considered missing values for inclusion/exclusion purposes as long as patients meet the complete case criteria. No imputation will be performed for vital sign data.

For features that are not vital signs (e.g. age, sex), we anticipate minimal missing data (as these variables are routinely collected), and assume missing at random. Due to the longitudinal data structure with correlated observations, we opted for a simpler method of imputation for the primary analysis. For features missing $< 1\%$, complete case analysis will be

performed; between 1-<10%, multiple imputation; above 10%, the feature would be excluded from the model and the reason for missing data will be investigated.

Data quality

The data quality of the CIHI vs. chart review results of the comorbidity information will be assessed by Pearson correlation, with chart review as the gold standard.

Cohort characteristics

Continuous data will be presented in mean (SD) if normal, and median (IQR) if non-normally distributed. Categorical data will be presented as frequency (%). The following characteristics will be presented as overall group, and stratified by MINS vs. no MINS:

- Age
- Gender
- American Society of Anesthesiologists' physical status classification (ASA)
- Type of anesthesia (general, neuraxial, peripheral, and/or sedation)
- RCRI score and categories: pre-existing TIA/CVA, insulin dependent diabetes, serum creatinine >177 mmol/L, coronary artery disease, congestive heart failure, and high risk surgery including intrathoracic, intraabdominal or suprainguinal vascular surgery
- Charlson Comorbidity Index (CCI) score and categories: history of MI, CHF, PVD, CVA/TIA, dementia, chronic pulmonary disease, connective tissue/rheumatic disease, peptic ulcer disease, liver disease, diabetes mellitus, hemiplegia/paraplegia, moderate to severe CKD, local/metastatic malignancy, AIDS/HIV
- Surgical service
- Duration of surgery
- Surgical priority: emergent/urgent vs. elective
- ICU admission preoperatively
- Cardiovascular medications preoperatively: Angiotensin II receptor blockers (ARBs), angiotensin-converting enzyme (ACE) inhibitor, and beta blockers (based on available names extracted from Cerner; may be missing medications that have been held and not restarted in hospital).
- Estimated blood loss
- Use of intraoperative/postoperative vasopressors/inotropes
Yes/no (received anything at all)
Small amount of intraoperative use (phenylephrine (<200 mcg) or ephedrine (<10 mg))
Significant only (i.e. exclude if small doses of phenylephrine (<200 mcg) or ephedrine (<10 mg))
- Laboratory preoperatively (30 days before surgery): NT-proBNP, hemoglobin, creatinine/GFR, troponin
- Respiratory rate
- Postoperative disposition (ward vs. HAU vs. ICU) - multiple entries possible; time of moving in/out of each unit
- Descriptive statistics of troponin as a continuous variable by postoperative days

- Diagnosis of myocardial infarction, MINS, and postoperative myocardial injury
- MINS troponin monitoring
 - o Duration (operative day to the last day of troponin measurement)
 - o Numbers of troponin testing done and frequency
 - o Time of MINS diagnosis (rule in vs. rule out), hours after end of operation as defined by the event of patient leaves the operating room
- Non-MINS causes of troponin elevation
 - o PE/DVT
 - o Sepsis
 - o Rapid atrial fibrillation
 - o Cardioversion < 24 hours
 - o Chronic elevation (excluded)
- Vitals monitoring
 - o Frequency (plot frequency vs. POD)
 - o Duration within POD3
- 30 Day in-hospital mortality

Also, descriptive summaries of the vital statistics as listed in Table 4 will be presented.

Data processing

The Cerner, Surginet, and chart review data will then be linked by de-identified Cerner study ID. The time series time stamps will be shifted to have the start of surgery as 00:00, Jan 1, 2020, in order to standardize the times for longitudinal modeling. Data will then be processed for removal of vital sign artefacts per the Multicentre Perioperative Outcomes Group protocol (35). To generate a final blood pressure dataset, if noninvasive blood pressure and invasive blood pressure are available during the same minute, then the measurement that is 1) not marked as artefact and 2) has a higher systolic blood pressure will be taken. Data will also be processed for calculation of RCRI, determination of the timing of MINS diagnosis, truncation of vital sign time series to the appropriate time stamp (see below), and calculation of duration under threshold of the time series to create vital sign summary variables as described in Table 4 for each postoperative day (0-<24h, 24-<48, 48-<72, and <72-96h after surgery end time). A formal chart review will also be performed to extract data not automatically retrieved from Cerner and Surginet, and verify data quality of automatically extracted comorbidities.

For modeling troponin as a continuous outcome, the vital sign time series will be truncated at the last troponin measurement within 3 days of surgery. For modeling the binary MINS outcome definitions the data will be truncated at the time of troponin laboratory diagnosis of the outcome event, postoperative day 3 (since the MINS protocol monitors for 3 days) or hospital discharge or death, whichever occurs first. All time measurements will be standardized as above in relation to the surgery start time.

Predictive Modeling Approaches

Approach I. Analysis using conventional longitudinal modeling (primary objective)

Data visualization

The initial exploratory analysis of the vital signs and troponin data involves time series visualizations and summaries to explore any potential patterns present in the data that may be associated with troponin quantiles or MINS or myocardial injury diagnosis. Spaghetti plots of the longitudinal data will be created for the outcome and vital signs variables, with lines colour-coded by troponin quantiles or MINS or myocardial injury diagnosis. Other relevant visualizations (scatterplots, boxplots, etc.) examining the associations between the troponin outcome and the vital signs variables will also be created.

Primary Modeling

The primary analysis will involve building a linear mixed effects model (with random intercepts) to predict the maximum daily troponin level between postoperative days 0 to 2 as the continuous outcome. The postoperative days 0, 1, and 2 accounts for approximately 40%, 40%, and 10% of MINS, respectively (4). Due to the limitations in retrospective data and the daily troponin monitoring, we will use day as a unit for time rather than hour to avoid overestimation of precision by readers.

For the primary and secondary models described in Objectives 1 and 2, an *a priori* list of predictors will be used: duration hypotension (summarized as a percentage of duration of MAP<75 mmHg in the duration of time modeled, e.g. postoperative day 1) age, sex, emergency surgery, RCRI, and postoperative GFR, as well as the postoperative day and the interaction between postoperative day and % duration MAP<75 mmHg as detailed below.

For longitudinal modeling, the vital signs data and troponin data will be aggregated to the day level, so that the model can predict at the daily temporal level. If there are multiple troponin measurements on the same day, the maximum will be taken. This aggregation of the data is necessary to account for the fact that the vital signs and troponin measurements are measured at irregular intervals (both across patients and data types), often due to the acting physician's response to the patient's condition. Additionally, due to this characteristic of the raw data, the vital signs predictors will be created such that they are standardized to be robust to the number of daily measurements performed (for example, by taking the percentage of day duration, NOT the total duration, of blood pressure below a specific threshold across all measurements during that day). A categorical time variable (representing the day of the measurement) will be included as a predictor within the model.

Due to the longitudinal nature of the data, we need to include random effects to adjust for the dependence between within-patient daily observations. Thus, at minimum, we intend to include a random intercept corresponding to each patient within the model. However, we may consider including random slopes based on what is observed in the exploratory analysis of the vital signs data, though this would be limited by sample size. Since the effect of a vital signs covariate may be different depending on the day of monitoring, we will investigate interactions between the time predictor and vital signs predictors. This will be performed for only a small number of key time-varying predictors to avoid overfitting, given that the total

number of terms within the model will increase by at least 3 (if the interacting vital signs predictor is continuous or binary) for each additional interaction term included.

Visualizations of the effect of each predictor on the response will also be generated, to further investigate their relationships within the context of the model.

To summarize, a simplified example of the primary linear mixed effects model would be: $\text{Troponin} = \text{intercept} + b1\text{BP_day0} + b2\text{day1} + b3\text{day2} + b4\text{BP_day1*day1} + b5\text{BP_day2*day2} + \text{error}$ (plus other non-BP fixed-effect covariates as listed above). An example interpretation would be $b1$ will correspond to the effect of BP on Day 0, $b4$ will correspond to the additional effect of BP on Day 1 (with respect to Day 0) and $b5$ will correspond to the additional effect of BP on Day 2 (with respect to Day 0). However, we will perform exploratory analysis to explore other forms of longitudinal modeling to select the best model based on discrimination and calibration.

Survival analysis will not be employed due to the small variance in the days for the outcome (days 0-2). Also, right censoring is assumed in survival analysis, which does not apply in our case of troponin rise postoperatively as the majority of patients will not have a troponin increase eventually.

Secondary, Sensitivity, and Exploratory Analyses

In addition to the above outlined primary statistical analysis, we intend to conduct additional secondary, sensitivity and exploratory analyses to address Objectives 2 to 4 to examine how well the model performs given the following changes:

- Introduction of transformations or natural cubic splines on continuous predictors or outcomes
- Modelling using a generalized linear mixed effects model for binary definitions of troponin increase (per AHA, as described above).
 - Different truncations of vital sign data stream prior to MINS diagnosis (e.g. no truncation, 12h before diagnosis)
 - If sample size allows: subgroup analysis involving only patients with preoperative troponin; subgroup analysis for patients who are in the intensive care unit perioperatively, as this represents a sicker population.
- Intraoperative only, postoperative only
- Further inclusion of additional predictors (e.g. % duration of $\text{HR} > 100$) from the available vital signs data
- Exploration of the incremental value of vital signs in addition to the RCRI or NT-proBNP in predicting MINS or myocardial injury
- Inclusion of information from postoperative day 3
- Delta troponin (change from preoperative troponin) using linear contrast

Model evaluation

To validate the performance of the linear mixed effects model specified in the primary statistical analysis plan, given the longitudinal nature of the data, a repeated patient-based 5-fold cross-validation will be performed with 100 repetitions (doi:

10.1093/gigascience/gix019). Patient-based record was chosen as record-wise cross validation tends to overestimate prediction accuracy compared to subject-wise cross validation. Note that when using a linear mixed effects model to predict troponin for “new”

patients (such as those in a held-out validation set), there are no unique random effects corresponding to those patients and so we are assuming the mean response for these “new” patients. A “patient-based” approach for the cross-validation approach is performed to avoid data leakage from the training set into the validation set (i.e. a patient’s measurements could potentially be present in both the training and validation sets). To quantify predictive performance, the root mean square error (RMSE) will be computed for each repetition, and the corresponding average and standard deviation of those performance measures will be reported. Marginal (i.e. fixed effects only) and conditional (i.e. fixed and random effects) R-squared (Nakagawa and Schielzeth R-squared, doi.org/10.1111/j.2041-210x.2012.00261.x) will be calculated. For assessment of calibration, the predicted values will be averaged across all repetitions (for each actual observation), and a calibration plot will be generated along with measures of the calibration intercept and slope.

For the models involving the binary outcomes of MINS diagnosis, a similar validation approach will be conducted. To assess discrimination, receiver operating characteristic curves (ROCs) will be generated and their area under the curves (AUCs) will be computed for each repetition, forming a distribution of AUCs. Precision-recall curves will also be considered due to the severe class imbalance present in the dataset. Pseudo R-squared will be computed. To assess calibration, the mean predicted class probability will be taken across all repetitions for each observation and then a decile calibration plot will be created, with corresponding calibration intercept and slope.

Decision curve analysis will be done to determine the net benefit of the various binary outcome models across various thresholds, as compared to ordering or not ordering troponin on everyone.

Parameter Count Based on Sample Size and Event Rate

To mitigate potential overfitting of the model onto the available data, we will aim to restrict the number of coefficient terms included within our linear mixed effects model to be at most 15 (i.e. 50 parameters per patient), and 8 variables for the generalized linear mixed effects models (i.e. 10 parameters per outcome event). As there is limited guidance for longitudinal prediction models, this is a choice justified based on a combination of the anticipated sample size, the presence of repeated measures, the modelling of a continuous outcome, the interest in examining interactions between vital signs predictors and the time predictor, and lastly to minimize uncertainty in the predictions.

Approach II. Machine learning exploratory analyses

Aim 1:

We will evaluate several strategies to determine the optimal integration of workflow for imputation and internal bootstrap validation for small medical datasets involving longitudinal data, including modeling vital signs as a time series vs. summary variable. The best performing workflow will be written as a function available on GitHub.

Aim 2:

We will evaluate unsupervised machine learning techniques to describe and cluster patterns of time series data. This would help with classification and prediction, visualization, and interpretability. Then, we will use supervised machine learning techniques to evaluate what patterns in the time series drove predictions in the models, and whether we can determine how much sooner the machine learning models were able to predict myocardial injury events prior to laboratory detection. The visualization codes will be wrapped into a Python package for visualization.

Aim 3:

To determine whether the predictive performance can be improved by using machine learning over traditional models, we will develop and internally validate machine learning models (including boosted trees and neural networks) to predict outcomes as described above, using time series or summary vital sign variables. The modeling is limited by the small sample size and class imbalance, and specific techniques will be explored including temporal-based resampling in the derivation set, one-class learners, and autoencoders.

Participant Confidentiality and Privacy

The dataset contains de-identified perioperative patients. Only those listed on this protocol will have access to the de-identified dataset for the duration of this project. The dataset created for the study will be saved in a password-protected file after the completion of the study or, if applicable, after the publication of study results (whichever happens later). At the end of 5 years, the data will be deleted permanently in accordance to UBC IT policy.

Potential for Risk and/or Harm

This study involves the secondary use of existing de-identified data, and no additional data will be collected. There is no foreseeable risk of the possible disclosure of any identifiable data because the current research will involve de-identified secondary data only.

Report of Findings

The findings from this research will be presented to the St. Paul's Hospital Anesthesia Department through a grand rounds presentation. In addition, there may be the opportunity to present this at an anesthesiology conference and produce a peer-reviewed publication from this data.

Data Dictionary

Source: Surginet extraction

Variable name	Legend	Reason for request
IDN	ID (deidentified)	To deidentify patients in the dataset
